Pharyngolaryngeal adverse events (laryngospasm, bronchospasm, nausea, vomiting, coughing, desaturation (SpO₂ <94) and re-intubation need will be observed in the operation room and PACU at 5, 15, 25 and 45 min. Sore throat, nausea, vomiting, dysphonia and dysphagia will be evaluated and recorded at 2, 4, 6, 12 and 24 hours postoperatively. Postoperative adverse effects will be evaluated as follows: laryngospasm; airway obstruction due to muscle rigidity in the chest and abdomen, Bronchospasm; especially during expiration, increased respiratory effort and wheezing. Dysphonia; difficulty in speech because of difficult speech or pain. Difficulty in swallowing; difficulty in swallowing or painful swallowing.

Sore-throat; it was defined as constant pain felt independently of swallowing. The evaluation was made with 0 ile10 numerical pain rating scale (NRS: Numeric Rating Scala). According to NRS, sore throat score will be evaluated as; 0-1: none, 2-4: mild, 5-7: intermediate and 8-10: severe.

5 point scale was used to determine the severity of nausea / vomiting. (0 = no nausea, 1 = mild nausea, 2 = moderate nausea, 3 = vomiting less than 2 times per hour, 4 = vomiting more than 2 times per hour).

Cough; cough in the postoperative period (less than 5 coughs will be ignored within the first minute after removal of the mask or tube, more than 5 coughs will be counted),

Statistical Analyzes

Type I error (alpha) 0.05, the power of the test (1-beta) 0.9, the primary output variable in the air (glottis / trachea) for the amount of blood effect of 0.71 and the alternative hypothesis (H1) is two-way to be found a significant difference using this test A total of 80 patients were required, with a minimum sample size of 40 in each group (*Kaplan A, Crosby GJ, Bhattacharyya N. Airway Protection and the Laryngeal Mask Airway in Sinus and Nasal Surgery. Laryngoscope 114: April 2004.*)

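### The nausea/vomiting scale has no grade for severe nausea without vomiting or for exactly two vomits per hour, and it does not define the period over which the hourly rate is counted

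*Combined protocol and SAP*

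**What the plan says.** All of this stands in the combined protocol and SAP.

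- **Purpose of the scale (Outcome Measures).** "5 point scale was used to determine the severity of nausea / vomiting".
- **Lower grades.** "0 = no nausea, 1 = mild nausea, 2 = moderate nausea".
- **Upper grades, from moderate nausea on.** "2 = moderate nausea, 3 = vomiting less than 2 times per hour, 4 = vomiting more than 2 times per hour".
- **Early checks.** Nausea and vomiting are in a list of adverse events that "will be observed in the operation room and PACU at 5, 15, 25 and 45 min".
- **Later checks.** "Sore throat, nausea, vomiting, dysphonia and dysphagia will be evaluated and recorded at 2, 4, 6, 12 and 24 hours postoperatively".
- **Primary outcome (Statistical Analyzes).** "the primary output variable in the air (glottis / trachea) for the amount of blood effect of 0.71". Nausea and vomiting are therefore not primary.

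The plan does not state the look-back period for the hourly rate, or which of the nine checks use the 5-point scale. The Statistical Analyzes section covers the sample size only, so it names no summary or comparison for this score.

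**The concern.** A severity scale should give every patient exactly one grade, and two raters who see the same patient should reach the same grade. This scale falls short in three ways.

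1. **No severe nausea.** The score steps from moderate nausea directly to vomiting. A patient with severe nausea who does not vomit is left blank or entered as 2, below a patient who vomits once with little nausea. The plan's other severity scales, for sore throat and for blood in the airway, both have a severe level.
2. **A hole between grades 3 and 4.** One is defined as below two per hour and the other as above two. Two per hour itself belongs to neither.
3. **No counting period.** A rate per hour needs a stated look-back when checks are minutes apart early on and hours apart later. Without one, raters may apply different rules.

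At stake is the quality of one of the postoperative comparisons between the laryngeal mask and the tube. The worst nausea state cannot be recorded, and some vomiting patients have no valid grade. Grades from different checks may not mean the same thing if someone later summarises them over 24 hours.

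**Working it through.** The plan gives no figure to reproduce here. The check maps vomit counts to grades under the possible readings of the hourly rate.

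**Inputs.** The check times are 5, 15, 25 and 45 min, then 2, 4, 6, 12 and 24 h (Outcome Measures). The grade rule is below 2 per hour = 3, above 2 per hour = 4. *Assumption:* both sets of times run from the same time zero.

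**Step 1: coverage, which holds under any reading.** Grades 0 to 2 are none, mild and moderate nausea, and grades 3 and 4 require vomiting. Severe nausea without vomiting meets no definition. A rate r = 2 satisfies neither r < 2 nor r > 2.

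**Step 2: reading A.** *Assumptions:* the rate is vomits since the previous check divided by the gap in hours, and the scale is used at every check.

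- Rate for one vomit = 1 / gap.
- Fewest vomits for grade 4 = (2 × gap, rounded down) + 1.

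| Check | Gap | Rate for one vomit (per hour) | Grade | Fewest vomits for grade 4 |
|---|---|---|---|---|
| 5 min | 5 min | 12 | 4 | 1 |
| 15 min | 10 min | 6 | 4 | 1 |
| 25 min | 10 min | 6 | 4 | 1 |
| 45 min | 20 min | 3 | 4 | 1 |
| 2 h | 75 min | 0.8 | 3 | 3 |
| 4 h | 2 h | 0.5 | 3 | 5 |
| 6 h | 2 h | 0.5 | 3 | 5 |
| 12 h | 6 h | 0.17 | 3 | 13 |
| 24 h | 12 h | 0.08 | 3 | 25 |

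Under this reading the ungraded count is 2 × gap where that is a whole number: 4 vomits in a 2 h gap (4 / 2 = 2 per hour), 12 in the 6 h gap and 24 in the 12 h gap.

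**Step 3: reading A, with the scale used only from 2 h on.** One vomit is grade 3 at all five checks, so the switch from 4 to 3 disappears. The count needed for grade 4 still rises with the gap, up to 25 at 24 h.

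**Step 4: reading B.** *Assumption:* vomits are counted within one fixed hour, such as the last or the worst hour. One vomit is grade 3, two have no grade and three are grade 4, at whatever check. The dependence on gap length disappears. The hole now falls on a patient who vomits twice in the counted hour.

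**Step 5: what a fixed hour leaves open.**

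- If it is the last hour, the later checks leave uncovered 15 min before the 2 h check, then 1, 1, 5 and 11 h: 0.25 + 1 + 1 + 5 + 11 = 18.25 of 24 h. At the checks up to 45 min, a full postoperative hour has not yet passed.
- If it is the worst hour, nothing is uncovered, but staff need the time of each vomit, which the plan does not ask them to record.

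**The case against.** A reader might infer that the plan grades vomiting over windows of 5 minutes to 12 hours, so that the same event receives different grades at different times and a difference between arms could be hidden or created. The documents do not support that.

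- **The gap reading is not in the text.** The scale and the check times are given in separate paragraphs, and nothing says the rate is divided by the gap. Reading one vomit in 5 minutes as 12 per hour is strained. The ordinary sense is how often the patient vomited in an hour, and on that sense the time dependence goes away. This stands.
- **Use of the scale in PACU is not in the text either.** The early list is of events to be observed, such as laryngospasm and re-intubation. If the scale starts at 2 h, one vomit is grade 3 at every check. This stands too.
- **Both arms share the check times.** A comparison at a given check remains like with like provided one counting rule is applied to both arms, so no bias between arms has been shown. This stands.
- **Nausea and vomiting are also listed as separate items, and grade 3 or above identifies vomiting.** Any vomiting over 24 hours could therefore largely be derived from the present form, apart from the hole at two per hour and any vomiting outside the look-back. This stands in part, because severe nausea still cannot be recovered from the score.
- **One sentence on the look-back and two repaired grades would be enough.** That would close the gaps. It would leave nausea intensity and vomiting frequency in one score, so the nausea of a patient who vomits would remain ungraded.

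None of this touches the two missing grades, which follow from the definitions alone.

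**Conclusion.** The concern holds in limited form.

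- **Certain from the text:** severe nausea without vomiting has no grade, exactly two vomits per hour has no grade, and the counting period is undefined.
- **Conditional:** one vomit is grade 4 up to 45 min and grade 3 from 2 h on only if the rate is taken over the gap since the last check, the scale is used at every check and both clocks share a time zero. The plan states none of these.

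How many patients would be affected cannot be computed, because the documents give no expected rates of severe nausea or of repeated vomiting. The consequence is lost or ambiguous grades on a non-primary outcome. It does not reach the primary outcome or the planned 40 patients per group. A cheap change to the form should be made, but the trial's main question does not depend on it.

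**What to change.** At each check, replace the single score with two items:

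1. worst nausea since the last check, on a 0-10 NRS (the scale type already used for sore throat);
2. number of vomiting episodes since the last check.

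State in the plan that the arms are compared on worst nausea over 0-24 h and on any vomiting over 0-24 h. The look-back is then fixed by the wording of the item, every state can be recorded, and no hourly rate is needed.

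If the 5-point scale is kept as description, add a grade for severe nausea, assign exactly two per hour to one of the two vomiting grades, state the counting window, and list the checks at which the scale is used.

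The cost is one changed line on the form, one sentence in the protocol, and less direct comparability with any study that used the 5-point scale. Treatment, primary outcome and sample size are unchanged.

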Title page

**Is Endotracheal Tube Use Mandatory in Patients Undergoing Nasal Septum Surgery?
Randomized, Controlled, Prospective Clinical Trial**

[name], Asst. [name] of Anesthesiology and Reanimation, Inonu University Medical Faculty, Malatya, Turkey

[name], Asst. [name] of Anesthesiology and Reanimation, Inonu University Medical Faculty, Malatya, Turkey

[name], Asst. [name] of Anesthesiology and Reanimation, Inonu University Medical Faculty, Malatya, Turkey

[name], [name] of Anesthesiology and Reanimation, Inonu University Medical Faculty, Malatya, Turkey

Address all correspondence to:

[name], Asst. [name] of Anesthesiology and Reanimation, Inonu University Medical Faculty, Malatya, Turkey

Mail: [contact]

[contact]

Protocol

This study is approved in Malatya Clinical Research Ethics Committee with the protocol code of 2018-165 and carried out at Department of Anesthesiology, Inonu University Medical Faculty in accordance with the criteria of Helsinki Agreement.

The study is planned as a prospective, randomized clinical trial. For randomization, the patients will be assigned to the study groups entirely by chance, and selection bias was prevented. MedCalc for Windows, version-16 statistical software (medcalc.com.tr.) will be used. A total of 80 patients with elective nasal septum surgery will be randomly assigned to the groups of Supreme LMA (Group L, n = 40) and ETT (Group E, n = 40).

Patients who agreed to participate voluntarily were informed about the potential risks and predictable outcomes of the study. The study will be performed on 80 patients between 18-65 years old, American Society of Anesthesiologists (ASA) I-II group planned for elective nasal septum surgery. Preoperative anesthesia evaluation (I) higher than ASA II (II) Patients with severe respiratory, hepatic or renal dysfunction (IV) Patients with history of allergy to anesthesia medications (V) of neurology and psychiatry patients (VI) Body mass index (BMI) of 30 Patients with obstructive airway history (cervical spine pathology, modified Mallampati grade 4 or thyromental distance <65 mm, VIII) will be excluded from the study who had a high risk of regurgitation or aspiration.

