Patients who opened their eyes with eye, breathing regularly, respiratory rate was 12-20 / min, oxygen saturation greater than 95% will be extubated and taken to the recovery room (PACU).

Outcome Measures

In Group L and E, oropharyngeal leak pressures will be measured while the head will be in neutral position. The flowmeter O₂ current will be set at 3 L / min and the expiratory valve will be closed. When an investigator who did not know which type of airway device was placed, another researcher looked at the current pressure value from the aneroid manometer and confirmed that the pressure remained constant (pressure gauge stability test). This value was recorded as the value of oropharyngeal leakage pressure. To prevent lung exposure to barotrauma, the expiratory valve was opened when the peak inspiratory pressure reached 40 cmH₂O, and the test will be terminated.

At the end of the surgery, in Group L and E, the presence of blood will be observed through a tubular fiberoptic bronchoscope. Posterior oropharynx will be carefully aspirated at the end of surgery in patients with endotracheal tube. After extubation, presence of blood around ETT cuff and distal blood will be examined. In the presence of blood, a four-scale scale will be used at the level of glottis-trachea and distal trachea. (1 = no, 2 = mild, 3 = moderate, 4 = severe). Mean arterial pressure (MAP), heart rate (HR), and peripheral oxygen saturation (SpO₂) immediately prior to anesthesia induction, 5, 15, 30, 45, 60 after confirmation of airway placement 75. EtCO₂ will be recorded per minute and every 15 minutes during the operation. Demographic data, duration of surgery and total anesthesia duration will be recorded.

Orogastric tube placement; very easy, easy, difficult, very difficult in the form of a 4-point scale will be used.

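### Does leaving the test for the primary blood score unnamed undermine the stated 90% power and the primary conclusion?

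*Combined protocol and SAP*

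**What the plan says.** The only statistical text is the sample-size sentence in the Statistical Analyzes section. It sets the error rates and the variable: "Type I error (alpha) 0.05, the power of the test (1-beta) 0.9, the primary output variable in the air (glottis / trachea". It then gives the effect and a two-sided alternative, "for the amount of blood effect of 0.71 and the alternative hypothesis (H1) is two-way to be found a significant difference using this test", and the result: "A total of 80 patients were required, with a minimum sample size of 40 in each group". The sentence refers to a test that has not been introduced. It does not say what kind of quantity 0.71 is.

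The Outcome Measures section describes the measurement. At the end of surgery "the presence of blood will be observed through a tubular fiberoptic bronchoscope", and where blood is present "a four-scale scale will be used at the level of glottis-trachea and distal trachea", with grades "1 = no, 2 = mild, 3 = moderate, 4 = severe".

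The Protocol section says that "MedCalc for Windows, version-16 statistical software (medcalc.com.tr.) will be used". That sentence stands in the randomisation paragraph and names no method of analysis.

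**The concern.** Power and false-positive rate are properties of a particular test. With none named, an analyst could compare ranks, compare mean scores, run a chi-square on four unordered grades, or reduce the score to any blood versus none. The stated 90% cannot hold for all of these.

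Two consequences would matter. A non-significant chi-square might be read as a null result at 90% power when its power was lower. And a test chosen after seeing the data could raise the false-positive rate: reporting the smaller of the rank and chi-square p values takes 5% to between 6.2% and 8.1% in simulation.

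A constructed dataset shows that verdicts can split. Take 40 per group in grades 1 to 4, with Group L 28/8/3/1 and Group E 19/11/6/4. The rank test gives p = 0.029 and the t-test 0.027, but the four-grade chi-square gives 0.17 and Fisher's exact test on presence gives 0.069.

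**Working it through.** **Inputs.** From the Statistical Analyzes section: two-sided 0.05, power 0.90, effect 0.71, 40 per group. From Outcome Measures: four ordered grades. The documents give no grade shares, so every set of shares below is an assumption.

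**1. The plan's own figure.** Read 0.71 as a standardised mean difference.

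- Normal approximation: n = 2 × (1.960 + 1.282)² / 0.71² = 2 × 10.507 / 0.5041 = 41.7, so 42 per group.
- Noncentrality at 40 per group: 40 × 0.71² / 2 = 10.08. Power is 88.8% by the normal approximation and 88.0% by the t-test.
- The t-test needs 42.7, so 43 per group, for 90%.
- A rank test with an assumed relative efficiency of 0.955 needs 42.7 / 0.955 = 44.7, so 45 per group. It has about 86.5% power at 40.

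The plan's 40 is therefore close to what a comparison of means gives, within about two points of power. The reading of 0.71 is itself an assumption.

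**2. The chi-square comparison.** Grant a 1-df test 90% power, which is noncentrality 10.507. A 3-df chi-square (critical value 7.815) with the same noncentrality has power 0.784. It needs 14.171 for 90%: 40 × 14.171 / 10.507 = 53.9, so 54 per group. Simulated proportional-odds shifts, tuned to 90% rank-test power, give chi-square power of 0.76 to 0.78.

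**3. Does that loss follow from 90% rank-test power alone?** No. It also needs the steady shift. Simulated power at 40 per group for other shapes:

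| Assumed grade shares (%) | Rank | Chi-square |
|---|---|---|
| 75/20/4/1 vs 37/58/4/1 | 0.90 | 0.91 |
| 75/20/4/1 vs 40/55/4/1 | 0.85 | 0.85 |
| 60/30/8/2 vs 40/20/10/30 | 0.79 | 0.92 |
| 50/40/10/0 vs 20/45/25/10 | 0.94 | 0.86 |

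The gap can persist, vanish or reverse, so neither 78% nor 54 per group is a property of this design.

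**4. Which tests does the text point to?** The primary variable is an amount, at the glottis/trachea. Outcome Measures grades that level in order, with absence as grade 1. An unordered chi-square discards the order. Presence versus absence discards the grading.

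Under steady shifts with the rank test at about 0.90, the t-test has 0.86 to 0.90. They separate more when the difference lies mainly between grades 1 and 2: for 75/20/4/1 against 40/55/4/1, rank has 0.85 and t has 0.72.

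**5. The illustration.**

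- Grade totals are 47, 19, 9 and 5, so expected counts per group are 23.5, 9.5, 4.5 and 2.5. Half of the eight cells fall below 5, so the chi-square approximation is doubtful here.
- Chi-square = 2 × (4.5²/23.5 + 1.5²/9.5 + 1.5²/4.5 + 1.5²/2.5) = 5.00 on 3 df, p = 0.17.
- Rank test: midranks 24, 57, 71 and 78 give a Group L rank sum of 28×24 + 8×57 + 3×71 + 78 = 1419, against 40 × 81 / 2 = 1620 expected. The tie-corrected standard error is 91.9, so z = −2.19, p = 0.029.
- t-test: means are 57/40 = 1.425 and 75/40 = 1.875, p = 0.027.

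The two tests that use the order of the grades agree. The tests that split from them are the two that set the order or the grading aside.

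**The case for a change.** The strongest case for acting is that this is a combined protocol and SAP, so no other supplied document names the test, and the sentence refers to a test that is not there. One added sentence would close the matter and would remove any suspicion that the test was picked after seeing the results. Even where rank and chi-square have equal power, their verdicts differ in about 10% of simulated trials. Under steady shifts they differ in 14% to 15%.

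The omission stands, and naming the test would be good practice. What does not stand is the size attached to it. The discordance and the 6.2% to 8.1% false-positive range compare the rank test with a test that ignores the order of the grades, which nothing in the documents suggests. The false-positive range also supposes that the investigators run both tests and report the smaller p value. Fisher power of 0.34 to 0.85 for presence versus absence rests on assumed shares and on treating presence of blood as a rival endpoint, when it introduces the grading. Nor does the point correct any rule or number in the plan: no arithmetic error in 40 per group is shown.

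**Conclusion.** The plan does not name its primary test, but no change follows. The outcome is an ordered four-grade score at a stated level, tested two-sided at 5%. An analyst who fills the gap in the ordinary way, with a tie-corrected rank test or a comparison of mean scores, reaches a sound result. If 0.71 is a standardised difference, power at 40 per group is about 88% by t-test and about 86% by rank test (relative efficiency 0.955 assumed). That is slightly below 90%, and exactly 90% with a rank test is not shown.

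The fall to about 76% to 78% needs both an unordered chi-square and a proportional-odds shift. The plan specifies neither. This conclusion rests on the analysis respecting the order of the grades. The rank test is the safer of the two natural choices where the difference sits mostly between no blood and mild.
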